**Outcome Measurement/Participation Timeline:** Participants will be randomized into immediate and waitlist treatment groups using permuted block randomization with stratification. Analysis between these two arms will be exploratory only in nature, and will inform us regarding the feasibility of the waitlist control design for use in a larger clinical trial. All participants will be evaluated before training begins, immediately following training, and at a 3-month follow-up. Participants in the delayed arm will participate in two pre-training evaluations, one immediately upon enrollment and one at the end of the delay period immediately before beginning training.

Week	1	2	3	4	5	6	7	8	9	10	11	12	13	
Immediate	Pre-training eval.	Skill 1	Skill 2	Skill 3	Skill 4	Skill 5	Post-training eval.							Follow-up eval. (week 19)
Waitlist	Pre-training eval.						Pre-training eval.	Skill 1	Skill 2	Skill 3	Skill 4	Skill 5	Post Training Eval.	Follow-up eval. (week 25)

**Statistical Considerations:** Primary outcome evaluation will be done with the entire sample of twenty. The mean pre-to-post-training change in each *ALA* domain score will be computed with the corresponding 90% confidence interval. With the total sample size of 20 subjects, the width of the two-sided 90% confidence interval is equal to 0.39 standard deviations of the pre-to-post-training changes. For the secondary analysis, we will evaluate the mean difference in each *ALA* domain scores between the immediate and delayed treatment arms at week 7 using the two-sided 90% confidence interval and two-sided two-sample t-test with alpha 0.1 (reflective of the small size pilot study). The results of comparison between the immediate and delayed treatment arms will be used to inform a future larger clinical trial. Qualitative data derived from narratives produced by PWA during administration of the PATD *ALA*-supplement will be orthographically-transcribed for offline analysis consistent with procedures detailed by Luck & Rose, 2007.

**Scientific rigor:** Participants will be assessed by a certified speech-language pathologist (SLP) who is not involved in PATD training. All assessment sessions will be video-recorded. A portion (approximately 20%) of the data will be selected for evaluation of intra- and inter-rater reliability. Inter-rater reliability will be conducted

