## Assessing an animal-assisted treatment program for adults with aphasia: the Persons with Aphasia Training Dogs (PATD) Program

Participants will be informed that they may withdraw from the study at any time, without penalty, and contact personnel are provided on the consent form. Participants will be informed that they can contact the PI at a later time if they would like to spend time reviewing the information in order to avoid them feeling pressured to participate. They will also be informed that pre- or post-consent screening or behavioral test results may indicate that they are not eligible to continue with the study. Pre-consent, research candidates from outside of the MRRI Research Registry will be screened to confirm diagnosis and related medical information and for geographic eligibility.

Assignment into each arm will be done using block randomization with stratification. Interested participants will be screened for one of two strata: 1) participation with a family dog or 2) participation through the Pennsylvania SPCA (PSPCA). Interested participants will be automatically assigned to the PSPCA condition if a) they do not have a family dog or b) their family dog is not eligible to participate. There will be no minimum requirement for assignment into either stratum.. As participants are enrolled in either the PATD or PATD-PSPCA condition, they will be block randomized into either immediate or waitlist treatment groups. Recruitment will be ongoing, until a minimum of ten PATD immediate and ten PATD waitlist participants have been enrolled.

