### Statistical Design and Power

For this feasibility study, we anticipate enrolling a minimum of twenty participants with stroke-aphasia.

Scores from weekly probes will allow for analysis of change in level of 'competence' over time, as determined using the *PPAHE* for that skill. For the purpose of statistical analyses of weekly evaluations, three scores (0="not ready", 1="ok", 2="best") will be dichotomized as competent (1 or 2) vs. not competent (0). In addition to the weekly evaluations, at the end of the training period, each participant will receive a summative score on the adapted *PPAHE*. This score may range from 0 to 10. For the primary analysis, the proportion of subjects that successfully completed the training will be quantified with the corresponding two-sided 90% exact binomial confidence interval. For the secondary analysis, (i) the median cumulative score will be computed with the corresponding two-sided 90% distribution-free confidence interval (Hahn & Meeker, 2011) and (ii) the weekly competence scores will be analyzed using the repeated measures logistic regression model. With the total sample size of 20 subjects, the width of the two-sided 90% exact binomial confidence interval is at most 0.38 if the observed proportion of subjects successfully completed the training is 0.5. The interval is narrower if the observed proportion of successes is higher (or lower) than 0.5.

The mean pre-to-post-training change in each ALA domain scores will be computed with the corresponding 90% confidence interval. With the total sample size of 20 subjects, the width of the two-sided 90% confidence interval is equal to 0.39 standard deviations of the pre-to-post-training changes. For the secondary analysis, we will evaluate the mean difference in each ALA domain scores between the immediate and delayed treatment arms at week 7 using the two-sided 90% confidence interval and two-sided two-sample t-test with alpha 0.1 (reflective of the small size pilot study). The results of comparison between the immediate and delayed treatment arms will be used to inform future larger studies. Qualitative data derived from narratives produced by PWA during administration of the PATD ALA-supplement will be orthographically-transcribed for offline analysis of themes discussed consistent with procedures detailed by Luck & Rose, 2007.

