To the extent that variation across the sample allows, we will explore the effects on performance of demographic (age, education) and aphasia-related (time post-onset, *WAB-R AQ*) variables. Due to the nature of the differences between PATD participation with a family dog and with shelter dogs, we will not run between-group analyses of PATD versus PATD-PSPCA participant groups.

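### The exploratory week-7 arm comparison ignores the dog stratum used in randomisation; to the extent that stratum predicts ALA score, its 90% interval is too wide and its test runs below alpha 0.1

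*Combined protocol and SAP*

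**What the plan says.** Under Specific Aim 2 (Outcome Measurement/Participation Timeline) the protocol states: "Participants will be randomized into immediate and waitlist treatment groups using permuted block randomization with stratification". The Recruitment section repeats this ("Assignment into each arm will be done using block randomization with stratification") and names the two strata: training with a family dog, or training through the Pennsylvania SPCA. People without an eligible family dog go to the PSPCA stratum. Stratum sizes are left open: "There will be no minimum requirement for assignment into either stratum". Enrolment continues "until a minimum of ten PATD immediate and ten PATD waitlist participants have been enrolled". Block size is not stated.

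The Statistical Considerations under Aim 2 and the Statistical Design and Power section both plan the arm comparison as the mean week-7 difference in each ALA domain score, "using the two-sided 90% confidence interval and two-sided two-sample t-test with alpha 0.1". Aim 2 calls this comparison exploratory and says its results will inform a larger trial.

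Statistical Design and Power also lists age, education, time post-onset and WAB-R AQ as variables to explore. Dog stratum is not on that list. The same section says "we will not run between-group analyses of PATD versus PATD-PSPCA participant groups".

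**The concern.** Blocking within strata keeps the mix of family-dog and shelter participants nearly equal in the two arms. A difference between strata in ALA score therefore contributes little to the arm difference. A plain two-sample t-test estimates its error variance as if allocation had been unrestricted, so the between-stratum spread stays in the standard error.

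If the strata differ on the ALA, the nominal 90% interval covers more than 90% of the time, the nominal 0.1 test rejects less often than 0.1 under the null, and some of the precision gained by stratifying is lost. The pooled SD would also overstate the within-stratum SD. That matters if it is carried into planning a larger trial that stratifies and adjusts in the same way.

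**Working it through.** **No stated figure to reproduce.** The documents give no power, detectable effect or interval width for the week-7 comparison.

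**Inputs from the documents.** Total N of 20, at least 10 per arm; two strata with no fixed sizes; two-sided alpha 0.1 and a 90% interval; two-sample t-test.

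**Inputs assumed.** Normal outcome with within-stratum SD of 1; stratum mean difference d = 0, 0.5, 1.0 or 1.5 SD; family-dog share from 10 to 16 of 20; blocks of 2 or 4.

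**Closed-form check, arms of 10 with each stratum split equally between arms.** Let p be the share in one stratum. Each arm's sum of squares gains 10·p(1−p)·d², so the expected pooled variance on 18 df is

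V = 1 + 20·p(1−p)·d²/18.

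The true variance of the arm difference is still 2/10. The planned half-width is about t(0.95, 18)·√(V·2/10). The stratum-adjusted half-width is about t(0.95, 17)·√(2/10). The quantiles are 1.734 and 1.740, so with V = 1 the multipliers are 0.775 and 0.778. The true error is approximately 2·P(T₁₈ > 1.734·√V).

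| Split | d | V | 1.734·√V | Approx. true error | Narrowing from adjustment |
|---|---|---|---|---|---|
| 10/10 | 0 | 1.000 | 1.734 | 0.100 | −0.3% (slightly wider) |
| 10/10 | 0.5 | 1.069 | 1.793 | 0.090 | 3.0% |
| 10/10 | 1.0 | 1.278 | 1.960 | 0.066 | 11.3% |
| 10/10 | 1.5 | 1.625 | 2.211 | 0.040 | 21.3% |
| 16/4 | 0.5 | 1.044 | 1.772 | 0.093 | 1.8% |
| 16/4 | 1.0 | 1.178 | 1.882 | 0.076 | 7.6% |
| 16/4 | 1.5 | 1.400 | 2.052 | 0.055 | 15.2% |

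Worked example, 10/10 and d = 1: V = 1 + 20·0.25/18 = 1.278. The width ratio is √1.278·0.775/0.778 = 1.127, and 1 − 1/1.127 = 11.3%.

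**Simulation with permuted blocks.** 20,000 trials per scenario, N = 20, splits 10/10, 12/8, 14/6 and 16/4. Blocks were of 4, and also of 2 for the 10/10 split. Planned t-test under no arm effect:

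- d = 0: error 0.098 to 0.102, coverage 0.898 to 0.902.
- d = 0.5: error 0.089 to 0.094, coverage 0.906 to 0.910.
- d = 1.0: error 0.066 to 0.077, coverage 0.923 to 0.934.
- d = 1.5: error 0.040 to 0.054, coverage 0.946 to 0.960.

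The model with arm plus stratum held error at 0.098 to 0.103 and mean width at 1.53 to 1.55 SD throughout. The t-test's mean width rose to as much as 1.59, 1.74 and 1.96 SD at d = 0.5, 1.0 and 1.5.

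**Power** for a true effect of 1 SD, 12/8 split, blocks of 4, t-test versus adjusted model: 0.696 v 0.694 (d = 0), 0.679 v 0.694 (0.5), 0.615 v 0.690 (1.0), 0.520 v 0.685 (1.5).

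**Very lopsided split, 18/2, blocks of 4** (12,000 trials per scenario). The t-test's error is 0.099 at d = 0.5 and 0.091 at d = 1.0. Adjustment widens the interval by about 2% at d = 0 and about 1% at d = 0.5, and narrows it by only 3% at d = 1.0. One reason is that both members of the small stratum can land in the same arm, so arm and stratum are then no longer balanced.

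**The case against.** The strongest reply is that the loss is conditional. A reader might infer that the planned interval and p-value are too conservative as a matter of fact. The documents do not support that. They report no ALA scores by stratum and no SD, and the remark that family-dog and shelter participation differ in nature concerns the setting, not the scores. With no stratum difference the t-test keeps its level. This stands, and the conclusion is worded accordingly.

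The larger losses need stratum differences of 1.0 to 1.5 SD, for which the documents offer no figure. At 0.5 SD the loss is slight, and because no minimum stratum size is set, an uneven split could shrink it further. This also stands.

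The comparison is exploratory, the primary analyses are single-group estimates that are unaffected, and the error does not create false positives. That limits the severity.

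A reader might also take the exclusion of PATD versus PATD-PSPCA analyses as forbidding a stratum term. The text rules out comparing the two groups and does not mention adjustment, so that reading is not established. A clarifying clause is enough.

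On the other side, a stratum difference is plausible. The ALA covers environment, relationships, community engagement and confidence. Shelter participants must complete orientation and show enough mobility and strength to handle a dog. The strata also differ in whether participants train with a dog of their own. Plausibility justifies a nearly free safeguard, but does not show that the loss will occur.

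**Conclusion.** The mismatch is in the text: allocation is stratified by dog status, and the one randomised comparison ignores it. The consequence is conditional on dog stratum predicting ALA score.

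For N = 20 and splits from 10/10 to 16/4, assumed stratum differences of 0, 0.5, 1.0 and 1.5 SD give a true error of about 0.10, 0.09, 0.07 to 0.08 and 0.04 to 0.05 against the nominal 0.1. The adjusted interval is narrower by about 0%, 2 to 3%, 8 to 11% and 16 to 21%. At 18/2 there is little to gain. These figures also rest on a normal outcome and on block sizes that the documents do not state.

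Severity is minor: the comparison is exploratory and any error is in the conservative direction.

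**What to change.** In the Aim 2 Statistical Considerations and in Statistical Design and Power, replace the two-sample t-test with a linear model of week-7 ALA domain score on arm plus dog stratum, and report the arm coefficient with its 90% interval and test at alpha 0.1. Add two clauses:

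- The stratum term is dropped if a stratum is empty or has too few participants to be represented in both arms. This is decided from the stratum counts alone, before outcomes are examined.
- The stratum term is an adjustment for the randomisation factor and is not the PATD versus PATD-PSPCA comparison that the plan excludes.

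The cost is one degree of freedom (half-width multiplier 0.775 to 0.778 SD with 10 per arm), a possible widening of about 2% if the split is very lopsided, and a few sentences of text. No extra data are needed.

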### Dissemination Plan

The PI will ensure that the clinical trial information, including descriptive information, recruitment information, location and contact information, and administrative data is registered with ClinicalTrials.gov within 21 days of

## Assessing an animal-assisted treatment program for adults with aphasia: the Persons with Aphasia Training Dogs (PATD) Program

enrollment of the first participant and that summary results information, including participant flow, demographic and baseline characteristics, outcomes and statistical analyses, adverse events, the protocol and statistical analysis plan, and administrative information is submitted to ClinicalTrials.gov within 12 months of the primary completion date. Informed consent documents will include a specific statement that de-identified study information and results will be posted to ClinicalTrials.gov. The Albert Einstein Health Network has an internal policy in place to ensure that clinical trials registration and results reporting occur in compliance with policy requirements.

